## **6.7 BASELINE, TIME WINDOWS AND CALCULATED VISITS**

Values observed at visit 1 will be considered as baseline assessment.

The medical records of patients belonging to Group B will be evaluated in the nintedanib treated arm till the date of start of their participation in this active surveillance program. Group B and Group C patients will be followed up according to clinical practice for at least 52 weeks or up to the discontinuation (whichever is earlier) from the start of the treatment at regular intervals (i.e. approximately every 4 weeks for the first 3 visits and approximately every 12 weeks thereafter till week 52).

There may be unscheduled visit(s) between the scheduled visits. In case the patient is lost to follow up (patient not contactable for further visits), the site should attempt to contact the patient telephonically to gather the information on the vital status and record it in the eCRF. Patients who are prescribed pirfenidone will not be followed.

## **7 PLANNED ANALYSIS**

- All study data will be included in individual patient study data listings. In general, all data will be listed by therapy prescribed and by visit (if applicable). The basic data like demographic and baseline characteristics, patient disposition and patient analysis set will be listed and also summarized by therapy prescribed, by Group. All summary tables will represent descriptive statistics for the parameters being analyzed, wherever applicable.
- Numeric presentations:
  - Non-integer numerical data should be presented with decimal point.
  - If the non-formatted data (e.g. which is received from the clinical database) is inconsistently presented, a decision on how to present the final data will be made on a case-by-case basis.
  - When rounding is required, number 4 or below will be rounded down and number 5 or above will be rounded up.
  - When deriving new variable(s) based on raw data, no rounding will be performed at intermediate calculation. Rounding will only be performed when displaying data.
  - Descriptive analysis for continuous data will include number of non-missing observations (n), mean, standard deviation (SD), median, minimum, maximum, Q1, and Q3. Means, medians, Q1 and Q3 will be rounded to 1 decimal place more than the original data. Standard deviation will be rounded to 2 decimals place more than the original data. Minimum and maximum will be displayed with the same decimal precision as the original data.
  - For categorical data, frequency and percentage with corresponding 95% confidence interval will be presented wherever applicable. Confidence interval and percentages will be rounded to 1 decimal place. Percentages equal to 100 will be output as '100'. The counts and percentages equal to 0 will be represented as '0' only.
- Missing data will not be imputed but will be analyzed as missing.

- Baseline assessments are the assessments taken at the Visit 1 for all patients. If there are multiple assessments collected on the same scheduled time, the average of these assessments will be used.
- The change from baseline is defined as the post-baseline value minus the baseline value.
- Text column should be left justified.
- All the data analysis will be done using SAS® version 9.4.

## **7.1 DEMOGRAPHIC AND OTHER BASELINE CHARACTERISTICS**

At visit 1, the baseline characteristics (e.g. demographics, pulmonary function tests, HRCT evaluation etc.,) will be recorded for all patients (either treated with nintedanib or pirfenidone) from the same centre during the same time period.

Demographic characteristics at visit 1 will be listed individually by therapy prescribed by Group by sites and patients. Age and time since IPF diagnosis calculated till the first exposure of study drug will be summarized using descriptive statistics. Gender (male and female), smoking status (Never Smoked, Ex-smoker, Current smoker, Unknown), alcohol consumption (Never, Former, Current, Unknown), cocaine (Never, Former, Current, Unknown), any other Drug Abuse (Yes/No), result of chest HRCT evaluation (UIP Pattern, Possible UIP Pattern, inconsistent UIP Pattern, Emphysema, Not available) and result of surgical lung biopsy (UIP Pattern, Probable UIP Pattern, Possible UIP Pattern, Inconsistent with UIP Pattern, Not available) will be summarized using frequency counts and percentages.

Symptoms of IPF (mMRC score) will be listed separately by therapy prescribed and by patients and summarized using frequency counts and percentages. The details about mMRC score are as follows:

Table 7.1: 1 The classification of mMRC dyspnea scale

Grade 0:	I only get breathless with strenuous exercise.
Grade 1:	I get short of breath when hurrying on the level or walking up a slight.
Grade 2:	I walk slower than people of the same age on the level because of breathlessness, or I have to stop for breath when walking on my own pace on the level.
Grade 3:	I stop for breath after walking about 100 meters or after a few minutes on the level.
Grade 4:	I am too breathless to leave the house or I am breathless when dressing or undressing.

## **7.2 CONCOMITANT DISEASES AND MEDICATION**

Relevant past or present medical history at visit 1 will be listed individually by therapy prescribed and by site and patient. Medical history data will be coded using Medical Dictionary for Regulatory Activities (MedDRA) version 20.0 or higher.

Concomitant medications will be coded using the World Health Organization Drug Dictionary (WHO DD), version June 2017 or later. It will be summarized using frequency counts and percentages as per ATC level 3 text and separate listing presented by therapy prescribed and by site and patient.

Prior IPF treatments (Pirfenidone or Other) for patients prescribed Nintedanib will be listed separately by site and patients.

## **7.3 TREATMENT COMPLIANCE**

No analysis planned for compliance of treatment.

## **7.4 PRIMARY OUTCOME(S)**

- Incidence of all ADRs in nintedanib treated patients:

The frequency with percentages and incidence rate of all ADRs in nintedanib treated patients will be tabulated by system organ class and preferred term.

The incidence rate will be presented as rate per 100 patient years along with 95% confidence interval.

➤ Incidence of all SAEs in nintedanib treated patients:

The frequency with percentages and incidence rate of SAEs will be tabulated by system organ class and preferred term.

The incidence rate will be presented as rate per 100 patient years along with 95% confidence interval.

All analyses of AEs will be based on the number of patients with AEs and not on the number of AEs.

### **Incidence Rate of AE**

Incidence rate is the number of new cases of an AE occurring in a specified time period divided by the cumulative time at risk.

### **Derivation of Time at Risk in Patients-years for a specific AE**

- Patients with specific AE:

Time at risk (AE) in days = (Start date of first specific AE - Treatment start date) +1

- Patients without specific AE:

Time at risk (AE) in days = Overall time at risk = (End date of time at risk - Treatment start date) +1

Total AE-specific time at risk is derived as below:

Time at risk (AE) [years] = Sum of time at risk [days] across all patients / 365.25

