10. RESEARCH METHODS

10.1 STUDY DESIGN

200 IPF patients treated with nintedanib per the Indian label will be enrolled in this active surveillance program. They are classified into following groups:

- Group A. Patients who started treatment with nintedanib after 23rd January, 2017 and have permanently discontinued the drug (as decided by the investigator) at the time of participation in the active surveillance. Data for these patients will be collected in anonymized manner after getting approval from the Ethics Committees for data collection and sharing.
- Group B. Patients who started treatment with nintedanib after 23rd January, 2017 and are continuing the drug at the time of participation in the active surveillance.
- Group C. Patients who have been newly prescribed nintedanib at the time of participation in the active surveillance.

In addition 200 IPF patients treated with pirfenidone will also be enrolled. They are classified into following groups:

- Group I. Patients who started treatment with pirfenidone after the 23rd January, 2017 and have permanently discontinued the drug (as decided by the investigator) at the time of participation in the active surveillance. Data for these patients will be collected in anonymized manner after getting approval from the Ethics Committees for data collection and sharing.
- Group II. Patients who started treatment with pirfenidone after the 23rd January, 2017 and are continuing the drug at the time of participation in the active surveillance.
- Group III. Patients who have been newly prescribed pirfenidone at the time of participation in the active surveillance.

The medical records at the selected sites will be screened to enroll Group A and B patients in a retrospective manner. Group C patients will be enrolled prospectively. The first patient enrolled at a given site should be in the nintedanib group. Once a patient is enrolled into the nintedanib group, the site team is suggested to enrol the next eligible patient, who has initiated or will be initiating pirfenidone at the same site in the pirfenidone group.

The safety data for nintedanib treated patients will be collected for at least 52 weeks or till the discontinuation of the drug, whichever is earlier. Patients treated with pirfenidone will not be followed.

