10.9 LIMITATIONS OF THE RESEARCH METHODS

The scientific objective of this active surveillance is to obtain an estimate of the occurrence of all ADRs and SAEs in IPF patients prescribed Nintedanib per the approved label in the real world setting. For retrospective data, there may be a possibility of missed information on adverse events. For patients followed prospectively, lost to follow up, loss of information and recall bias could impose limitations. Since only the cohort treated with Nintedanib will be followed up, it is impossible to assess the safety of Nintedanib compared to other drugs. The possible selection bias will be minimised by enrolling all patients who have initiated or will initiate nintedanib (Group A, B and C) from the date of commercial availability of drug (23rd January 2017) at selected centres and potential channelling bias will be assessed by recording the baseline characteristics of a comparator group of equal number of patients who have been treated with pirfenidone.

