## **6 GENERAL ANALYSIS DEFINITIONS**

### **6.1 TREATMENT**

This active surveillance will include 200 IPF patients treated with nintedanib per the Indian label. They are classified into following groups:

Group B:	Patients who started treatment with nintedanib after 23rd January, 2017 and are continuing the drug at the time of participation in the active surveillance.
Group C:	Patients who have been newly prescribed nintedanib at the time of participation in the active surveillance.

In addition 200 IPF patients treated with pirfenidone will also be enrolled. They are classified into following groups:

Group II:	Patients who started treatment with pirfenidone after the 23rd January, 2017 and are continuing the drug at the time of participation in the active surveillance.
Group III:	Patients who have been newly prescribed pirfenidone at the time of participation in the active surveillance.

The medical records at the selected sites will be screened to enroll Group B patients in a retrospective manner till the date of start of their participation in this active surveillance program and prospectively thereafter. Group C patients will be enrolled prospectively. The first patient enrolled at a given site should be in the nintedanib group. Once a patient is enrolled into the nintedanib group, the site team is suggested to enroll the next eligible patient, who has initiated or will be initiating pirfenidone at the same site in the pirfenidone group.

As this is an active surveillance of patients prescribed nintedanib in the real world, no specific treatment is mandated or withheld from the patients. The choice of maintenance treatment for IPF must be according to regular medical practice and at the discretion of the physician. As for any active surveillance study, the assignment of the patient to nintedanib

or any other treatment falls within current practice and prior to the decision to talk to the patient about the study, so that the decision to prescribe nintedanib is clearly separated from the decision to include the patient in this active surveillance. The decision of treatment, including the intended duration of treatment, is at the discretion of the physician providing care for the patient.

Patients who have taken at least one dose of nintedanib will be included in the safety analysis.

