### **7.5.2 (Other) Secondary outcome(s)**

Frequency and percentage of patients who require dose reductions, interruptions and discontinuation due to adverse events will be presented separately by system organ class and preferred term.

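### The SAP analyses Group B (patients still on nintedanib at enrolment) from treatment start, pools them with new starters and omits Group A, so the discontinuation figures are biased downward

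*SAP*

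**What the plan says.** Protocol 10.1 defines three nintedanib groups. Group A started after 23 January 2017 and "have permanently discontinued the drug (as decided by the investigator) at the time of participation in the active surveillance". Group B started after the same date but "are continuing the drug at the time of participation in the active surveillance". Group C is "Patients who have been newly prescribed nintedanib at the time of participation in the active surveillance". Protocol 10.9 intends every starter since launch at the selected centres to be enrolled, across all three groups.

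SAP 6.1 lists only Groups B and C, while SAP 4 states that the planned analysis is unchanged from protocol version 5.0. The analysis sets in SAP 6.3 start from a signed consent form, and violation A1.2 in SAP 6.2 removes anyone without one from all sets. Protocol 10.10.1.1 asks for consent from Groups B and C but not from Group A, so a Group A patient would drop out of every set even if enrolled.

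SAP 7.4 starts the clock at treatment start for everyone. For patients without the event, "Time at risk (AE) in days = Overall time at risk = (End date of time at risk - Treatment start date) +1". All primary and secondary outcomes use one Treated Set (SAP 6.3). SAP 7.5.2 reports "Frequency and percentage of patients who require dose reductions, interruptions and discontinuation due to adverse events", and SAP 7.8.1 adds an incidence rate with a confidence interval for each of these.

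SAP 7 limits summaries by Group to basic data: "demographic and baseline characteristics, patient disposition and patient analysis set will be listed and also summarized by therapy prescribed, by Group". The visible outcome sections (7.4, 7.5.2, 7.8.1) have no split by Group. Protocol 10.9 concedes: "For retrospective data, there may be a possibility of missed information on adverse events". It does not mention that Group B is selected for still being on treatment.

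**The concern.** A Group B patient is in the study only because treatment had not ended before the site enrolled them. Between treatment start and enrolment, permanent discontinuation and death are impossible by definition. The SAP still counts that time as time at risk and counts the patient in the denominator of the percentage. Those who started at the same time and did stop are Group A, which the SAP leaves out. The numerator loses early stoppers while the denominator keeps the time of those who did not stop.

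This affects three results: the percentage of patients discontinuing because of adverse events, the matching incidence rate, and the rates of ADRs and SAEs that were fatal or ended treatment. All move towards better tolerability.

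For ADRs and SAEs that leave the patient on drug, and for dose reductions and interruptions, the event can be found in the chart and dated before enrolment. The concern there is different: time abstracted from charts, which the protocol says may miss events, is merged with prospectively observed time in one rate.

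At stake is the main tolerability figure of a study requested by the Indian regulator, when only 20 Indian patients had received nintedanib in the two phase III trials (protocol 8).

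**Working it through.** The documents give no expected rate, event count or power, and the 200 is a regulatory request (protocol 10.5), so there is no planned figure to reproduce.

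**Inputs from the documents.** Entry conditions for Groups B and C (SAP 6.1); clock from treatment start (SAP 7.4); 52-week window (SAP 7.7); earliest start 23 January 2017; protocol amendment 4 on 1 August 2018.

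**Assumptions.** True 52-week risk of discontinuation due to adverse events F = 20% (range 10–30%); Group B share s = 50% (range 25–75%); constant hazard; no other reason for stopping; start dates uniform over the L weeks before enrolment.

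**How long the lag can be.** 23 January 2017 to 1 August 2018 is 555 days, about 79 weeks. (555 − 364)/555 = 34% of that window lies at least 52 weeks back. This is a share of calendar days, not of patients.

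**Percentage.** Hazard h = −ln(0.8)/52 = 0.00429 per week and S(t) = exp(−ht). A Group B patient with lag t is drawn with weight S(t) and has remaining risk 1 − S(52)/S(t) if t < 52, and zero otherwise. With m = min(L, 52):

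Group B risk = [∫₀ᵐ S(t)dt − 0.8m] / ∫₀ᴸ S(t)dt; pooled = s × Group B + (1 − s) × 20%.

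| L (weeks) | Numerator | Denominator | Group B | Pooled, s = 50% |
|---|---|---|---|---|
| 13 | 12.644 − 10.400 = 2.244 | 12.644 | 17.7% | 18.9% |
| 26 | 24.602 − 20.800 = 3.802 | 24.602 | 15.5% | 17.7% |
| 79 | 46.607 − 41.600 = 5.007 | 67.002 | 7.5% | 13.7% |

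At L = 79, Group B shares of 25% and 75% give 16.9% and 10.6%. At half Group B, a true 10% becomes 6.7% and a true 30% becomes 21.0%. If half the hazard falls in the first 12 weeks, a true 20% becomes 12.7%.

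**Rate, with a fixed lag of 26 weeks and half Group B.**
- Group C: risk 0.200; mean time 46.607 weeks = 0.893 years; true rate 100 × 0.200/0.893 = 22.4 per 100 patient-years.
- Group B: risk 1 − 0.8/0.8944 = 0.1056; time from treatment start 26 + 24.602 = 50.602 weeks = 0.970 years.
- SAP method: percentage (0.1056 + 0.200)/2 = 15.3%; rate 100 × (0.1056 + 0.200)/(0.970 + 0.893) = 16.4.
- Group B clock started at enrolment (24.602 weeks = 0.471 years): 100 × 0.3056/(0.471 + 0.893) = 22.4.
- Front-loaded hazard (Weibull, shape 0.6): the SAP method gives 13.7% and 14.8, against a true 20% and 23.0. Delayed entry gives 20.3, which is closer but not exact.

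**If Group A is present.** Take 100 starters, all enrolled at 26 weeks. Group A holds 10.56 events and Group B later adds 9.44, making 20. With every clock at treatment start, time is 100 × 46.607 weeks and the rate is the true 22.4. If Group B's clock is moved to enrolment while Group A's events are kept, time falls to 134.7 + 2,200.5 = 2,335.2 weeks = 44.75 years, and the rate becomes 100 × 20/44.75 = 44.7, about double the truth.

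**ADRs that do not end treatment.** With complete charts the ratio of the SAP rate to the true rate is 1.00. Assume a true 52-week ADR risk of 60%, half Group B, a 26-week lag, and charts that record each event with probability 90%, 70% or 50%. The pooled rate is then 89.1, 83.4 or 77.5 per 100 patient-years, against a true 91.9.

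**The case against.** The strongest reply is that the protocol already contains the cure. Protocol 10.9 plans to enrol all starters in Groups A, B and C. If that happened and Group A were analysed, nobody would be selected for still being on treatment, and the bias would largely go, as the Group A calculation shows. This stands. It would be wrong to infer that restoring Group A achieves nothing. What remains is that protocol 10.2.2.2 closes enrolment at 200 with no order or quota between groups, so complete enrolment of A and B is not assured, and that the SAP as written has no Group A.

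A reader might also infer that the time-at-risk formula distorts every ADR and SAE rate. It does not. With complete charts it is harmless for events that leave the patient on drug, and two of the three parts of the secondary outcome, dose reduction and interruption, can be found in the chart.

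Nor do the documents support saying that the study answers its question mainly for patients who tolerated the drug. That needs a Group B majority, and no split is given. Missed chart events are a disclosed limitation, and AEs are listed for each patient, so some separation by hand is possible.

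Finally, several SAP sections are redacted. An analysis by Group may sit there, so the statement about missing splits covers visible text only.

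**Conclusion.** The point holds for the visible SAP. Discontinuation due to adverse events, as a percentage and as a rate, is biased downward by construction whenever any Group B patient has time on drug before enrolment and Group A is left out. The same applies to rates of fatal or treatment-ending ADRs and SAEs. The direction needs no assumption beyond the SAP's own definitions.

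The size does. It depends on the Group B share, the lag from start to enrolment and the shape of the hazard, none of which the documents give. The effect is about one percentage point in 20 if lags stay under 13 weeks, and about six points if they spread over the whole 79 weeks, both with half the patients in Group B and a constant hazard. The 79-week case is one scenario and not a forecast.

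For the remaining ADRs and SAEs, and for dose reductions and interruptions, the finding is only that chart-abstracted and prospective time are pooled without a split.

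**What to change.** 1. Reconcile SAP 6.1, 6.2 and 6.3 with protocol 10.1 and 10.9. Either restore Group A to the analysis sets, with set definitions that do not require consent from patients of whom the protocol does not ask it, or declare the omission in SAP 4 as a change and state its effect on the discontinuation outcome.
2. In SAP 7.4, 7.5.2 and 7.8.1, tabulate all primary and secondary outcomes by Group beside the total, and name Group C as the estimate free of this selection.
3. For ADRs and SAEs, show Group B events and person-time separately before and after enrolment.
4. If a pooled B+C figure for discontinuation or fatal events is kept without Group A, let Group B enter at enrolment (left truncation). Take the percentage from a left-truncated cumulative incidence, because delayed entry in the formula corrects only the rate. Do not pool delayed-entry Group B with Group A events.

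The cost is SAP wording and some table columns. Start date, consent date and Group are already needed for planned analyses, so no new data are required. The price is wider intervals for the Group-specific estimates and, probably, a less favourable discontinuation figure.

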### **Derivation of Incidence Rate of AE**

Incidence rate [1/100 patient-years (pt-yrs)] = 100\* number of patients with AE/ Time at risk (AE) [years]

The Incidence rate is based only on the first onset of an event in case of when patient may have multiple events during the trial.

The confidence interval for incidence rate can be estimated under assumption that the number of events occurring in a fixed interval of time follows a poisson distribution.

Incidence rate and its relevant confidence interval can be estimated using *Proc genmod* or exact method in SAS or other appropriate program.

Example:

1. *Proc Genmod*:

```
proc genmod data=<data-set>;
  model c = / offset=ln dist=poisson lrci;
  Estimate 'Mean' intercept 1 ;
  run;
```

(Note: c=number of new cases, ln=log transformed person-year)

OR

2. Exact method for 95% CI:

LCL= (quantile( 'chisq', 0.025, (Number of new cases\*2))/(person-years\*2))\*100

UCL= (quantile( 'chisq', 0.975, ((Number of new cases+1)\*2))/(person-years\*2))\*100

